# 1.5.4.1.1 Calibration

Speech perception will be calibrated using a calibration tone (or calibration sound file). A sound-level meter will be used to measure the dBC level of the calibration tone at a distance of 1 meter from the loudspeaker. The loudness will be adjusted through the audiometer or receiver to achieve the desired loudness level for the specific test.

- 1.5.4.2 Speech and Language Testing all administered in the bilateral listening condition
  - Vocalizations/speech samples as described above in baseline/pre-operative testing will be collected.
  - MacArthur Communicative Developmental Inventories (CDI) and the Minnesota Child Development Inventory (MinnCDI, Ireton & Thwing, 1974) as described above in baseline/pre-operative testing will be collected.
  - The Preschool Language Scale-3 (PLS-3), (Zimmerman, Steiner, & Pond, 1992) as described above in baseline/pre-operative testing will be collected.
  - Peabody Picture Vocabulary Development Scale (PPVT). The PPVT (Dunn & Dunn, 1997) is a standardized, norm-referenced measure of receptive vocabulary skills. The test is a multiple-choice measure consisting of sets of four black and white line drawings. The examiner names one of the pictures and the test recipient is expected to indicate which picture has been labeled, either verbally or through pointing.

- Expressive Vocabulary Test. This is an expressive vocabulary test that provides an index of expressive vocabulary skill.
- Goldman-Fristoe Test of Articulation-2 (Goldman & Fristoe, 2000). The GFTA-2 is a standardized, norm-based articulation measure that samples spontaneous sound production. Children are asked to respond to picture plates and verbal cues from the examiner with single words that test consonant accuracy in initial, medial, and final positions. This measure has norms based on the performance of normal-hearing children from age 2 years to 21 years.

# 1.5.5 Psychophysical and Electrical Impedance Measurements:

The following psychophysical and electrical impedance measurements will be attempted at 4, 8, 12, 18, 24 months, and annually thereafter through five years of age.

- 1. Electrical thresholds measured in current level.
- 2. Electrical maximum comfort levels measured in current level.
- 3. Impedance telemetry results using common ground (CG) and monopolar (MP1, MP2, MP1+2) stimulation modes.

## 1.6 Adverse Effects

Adverse effects are any undesirable clinical or medical occurrence associated with use of the device or participation in the study. Any adverse effects are to be reported to the FDA and our IRB via the "Adverse Effects Form". The Primary Investigator will be required to verify that there are or there are no adverse effects to report.

Adverse effects will be reported if observed, even if acknowledged as risk factors in the consent. Adverse effects include:

- 1. Vertigo, dizziness, or balance problems that did not exist preoperatively or worsened postoperatively
- 2. Facial nerve problems
- 3. Meningitis
- 4. Perilymphatic fistulae
- 5. Tinnitus that did not exist preoperatively or worsened postoperatively
- 6. Implant Migration/Extrusion
- 7. Skin flap problems
- 8. Device-related/programming problems
- 9. Infection requiring explantation
- 10. Device failure requiring explantation

# 1.7 Unanticipated Adverse Events

Unanticipated adverse device effects refer to any event not identified above that represents a "serious adverse effect on health or safety or any life-threatening problem or death caused by, or associated with, a device if that effect, problem or death was not previously identified in nature, severity, or degree of incidence in the investigational plan or application, or any other unanticipated serious problem associated with a device that relates to the rights, safety, or welfare of subjects." [FDA 21 CFR 812.3(s)]

Investigators are to inform their respective Institutional Review Boards (IRBs) immediately if an unanticipated adverse device effect is suspected (no more than 10 working days after the investigator learns of the effect). If the case is determined to be an unanticipated adverse device effect, the investigator will fill out an "Unanticipated Adverse Device Effect Form." University of Iowa will report the results of an evaluation of the unanticipated adverse device effect to the FDA and all other reviewing IRBs and investigators within 10 working days after first receiving notice of the event.

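### Section 1.7 confines unanticipated device effects to unlisted events, so a serious event of a type listed in 1.6 misses the timed evaluation even if its severity or frequency was unforeseen

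*Combined protocol and SAP*

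**What the plan says.** Section 1.6 (Adverse Effects) lists ten kinds of event. They range from balance problems and tinnitus, through meningitis, facial nerve problems and implant migration or extrusion, to infection and device failure that lead to explantation. One item is open-ended: "Device-related/programming problems". The section directs that "Any adverse effects are to be reported to the FDA and our IRB via the" Adverse Effects Form, and adds: "Adverse effects will be reported if observed, even if acknowledged as risk factors in the consent". It sets no deadline and no evaluation step.

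Section 1.7 (Unanticipated Adverse Events) begins: "Unanticipated adverse device effects refer to any event not identified above that represents". It then quotes the definition in 21 CFR 812.3(s), which applies "if that effect, problem or death was not previously identified in nature, severity, or degree of incidence in the investigational plan or application". Its second paragraph sets the procedure. The investigator informs the IRB immediately on suspicion, and "no more than 10 working days after the investigator learns of the effect". If the event is confirmed, the University of Iowa reports the results of an evaluation to the FDA and to all other reviewing IRBs and investigators "within 10 working days after first receiving notice of the event".

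**The concern.** The opening clause of 1.7 and the regulation it quotes use different tests. The clause asks whether the event has been named. The regulation asks whether the effect was identified in its nature, its severity and its frequency. Because the clause comes first and lies outside the quotation, it acts as a gate: an event that fails it never reaches the regulatory test.

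The listed types include some of the gravest foreseeable harms of this surgery in children aged 12 to 24 months. With at most 15 infants to be implanted, the whole safety experience will be a handful of events. A serious event of a listed type that turns out worse or more frequent than foreseen is one that the quoted definition is built to catch. At stake is whether it is evaluated, and its evaluation circulated, on a fixed clock.

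**Working it through.** No arithmetic applies, and the plan gives no figure to reproduce. The check is a comparison of the two sections.

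**Step 1: the structure of the definition.** As written, an event must satisfy both conditions:

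- (a) it is not identified above; and
- (b) it falls within the quoted regulatory text.

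**Step 2: apply it to a listed type.** Take a serious case of meningitis with an unforeseen course, or device failures requiring explantation at an unforeseen frequency. Under (b) alone either could qualify, because severity or frequency was not identified in advance. Under (a) both fail, because the type is on the 1.6 list. The severity and frequency limbs of the quotation therefore cannot operate for listed types.

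**Step 3: see what the 1.6 list identifies.** No item has an expected frequency. Only the two explantation items say anything about how grave the event is. The consent risks in 1.4.1 are likewise only named. So 'above' points to a list of types, not to a description of expected severity or incidence.

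**Step 4: compare the two routes.**

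| | Listed event, 1.6 | Event meeting the 1.7 definition |
|---|---|---|
| Reported to the FDA and IRB | Yes | Yes |
| Time limit | None stated | Immediate IRB notice, at most 10 working days; evaluation results within 10 working days |
| Evaluation of the event | None stated | Yes |
| Notice to other reviewing IRBs and investigators | None stated | Yes |

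**Step 5: look for another timed route.** No other section of the document supplies a deadline or an evaluation for adverse events.

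**Step 6: mark the boundary.** The quoted definition covers only serious or life-threatening effects, death, and other serious problems. A mild or routine instance of a listed item would fall outside 1.7 whether or not the three words are there.

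**The case against.** The best defence is that the sentence can be read coherently. It does not define 'identified', but the regulation quoted in the same sentence does so by reference to nature, severity and incidence. If that meaning is carried back to the opening clause, an event of unforeseen severity has not been identified, and the conflict disappears. This reading is available, but the protocol does not adopt it. The natural reference of 'above' is the numbered list immediately before, which is a list of types. A person classifying an event should not have to choose between two halves of one sentence.

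A second defence is that expected severities and frequencies may be given in the IDE application, which is not among the documents. That may be so, but the opening clause is applied first and would exclude the event before the application was consulted.

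Several stronger conclusions might be inferred, and the documents do not support them:

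- *That the quoted regulation itself requires the timed route.* The quoted text is only a definition. The 10-working-day steps are set out in the protocol's next paragraph.
- *That listed events go unreported.* Section 1.6 sends them to the FDA and IRB, and requires the Primary Investigator to verify whether there are any to report.
- *That every occurrence in all ten categories is affected.* Only serious occurrences are.
- *That a death following a listed event would be classed as anticipated.* Death is not on the 1.6 list, and the quoted definition names it separately. Such a death could be read as not identified above, so this consequence rests on one reading.
- *That some particular count among 15 infants shows the size of the fault.* The documents give no expected rate, so a proportion has nothing to be compared with.

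**Conclusion.** The point holds in limited form. Read plainly, 1.7 narrows the definition it quotes: a serious event whose type is listed in 1.6 cannot be an unanticipated adverse device effect, even when its severity or frequency was not foreseen. The loss is the time limit, the evaluation and the wider notification. Reporting to the FDA and IRB remains.

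The rule is wrong as written; it is not a case of missing detail. It belongs to safety reporting. No endpoint, estimate, sample size or analysis is touched, and no numerical size can be attached to it.

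The conclusion rests on two assumptions: that 'above' refers to the listed types, and that both conditions in the sentence must be met. If the sponsor intends the quoted regulation to prevail, the text should say so, and the same edit achieves it.

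**What to change.** Delete 'not identified above' from the first sentence of 1.7, so that the quoted definition alone decides what is unanticipated. This removes the conflict, and nothing further is strictly needed.

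If a clarification is wanted, it could say that listing an effect in 1.6 does not by itself make a serious occurrence anticipated when its severity or degree of incidence was not identified in the plan or the application. Any such sentence should keep the restriction to serious events, and should refer to the application as well as the plan. Without the first, frequent minor effects such as programming problems would be drawn into 1.7. Without the second, the test would be narrower than the quoted definition. Nor should it set a comparison against severities or frequencies described in 1.6, which states no frequencies and almost nothing on severity.

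The cost is three words in the protocol and possibly a few more serious events evaluated within 10 working days. Data collection and analysis do not change.

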# 1.8 Data Analysis

In order to assess the feasibility of using the Nucleus L24 electrode and the standardlength arrays on contralateral ears, data will be analyzed individually and with group statistics. Because the children implanted in this study will be 12-24 months of age at time of implantation, outcomes as to the success of this study may become clearer as the child ages and their speech and language skills develop. Thus, our primary measure of assessment will change as the child becomes older.

We will measure success of this study by assessing speech perception and speech/language development as described above in the test descriptions (see 1.5.4). We will attempt to compare these results with age-matched children implanted with standard-length bilateral devices on both ears on the same speech perception and speech/language measures. In addition, if possible, we will attempt to compare the same speech perception and speech/language measures on age-matched children implanted with a standard-length device on one ear and a Nucleus S12 implant on the contralateral ear. The independent variable will be whether the child receives Nucleus L24 and standard-length device on one ear and a Nucleus S12 implant on the contralateral ear. The dependent variables will be a set of speech perception and speech/language measures suitable for tracking growth of these traits.

Because this is a feasibility study, we will only be implanting up to 15 infants with Nucleus L24 and standard-length electrode arrays on contralateral ears. We recognize that this small number of subjects may not afford us enough statistical power to adequately answer all questions associated with using these different length electrode arrays in pediatric subjects who have bilateral profound hearing loss. However, it may lend us foundational knowledge to assess whether the device configurations can provide useful bilateral hearing while possibly preserving the scala media, organ of Corti and supporting cells of the ear for future advances in molecular and/or genetic treatments of the inner ear.

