### Investigational Protocol: Iowa Cochlear Implant Clinical Research Center Hybrid L24 and Standard Cochlear Implants in Profoundly Deaf Infants

## 1 INVESTIGATIONAL PROTOCOL

The purpose of this feasibility study is to evaluate whether a Nucleus L24 and a FDA approved standard-length device in the contralateral ear can provide useful binaural hearing in pediatric subjects who have bilateral profound hearing loss, meeting the criteria for cochlear implantation. Unlike a conventional cochlear implant, the Nucleus L24 is designed to preserve the regions of the cochlear partition that are apical to the electrode, thus leaving them available for possible future advances in the field of otolaryngology and hearing devices, such as mammalian hair cell regeneration techniques or improved implantable hearing devices. The Nucleus L24 (16 mm) array stimulates the basal turn of the cochlea, in an attempt to preserve the middle and apical regions of the scala media.

Criterion for selection of the Nucleus L24 and a standard-length device group will be parent interest in bilateral implantation and the following criteria: profound bilateral sensorineural hearing loss; lack of benefit from appropriately fit binaural hearing aids worn on a full-time basis; language deficit; and supportive family dynamics. Qualified participants must also meet the following criteria for inclusion and exclusion, respectively.

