### 1.1 Criteria for Inclusion:

- 1. Twelve to twenty-four months of age at the time of implantation.
- 2. Audiometric thresholds for frequencies 250 to 8000 Hz in the profound hearing range bilaterally. The type of hearing loss must be categorized as sensorineural in nature.
- 3. English spoken as a primary language (mono-lingual English-speaking family, where English is the primary language).
- 4. Willingness to comply with all study requirements.
- 5. Minimum of three-month hearing aid trial with appropriately fit hearing aids.
- 6. Patent cochlea and normal cochlear anatomy as shown by a CT scan. It is standard clinical practice to perform a CT scan on any patient pursuing cochlear implantation.

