### **1.2 Criteria for Exclusion:**

- 1. Medical or psychological conditions that contraindicate undergoing surgery.
- 2. Ossification or any other cochlear anomaly that might prevent complete insertion of the electrode array.
- 3. Developmental disabilities or other conditions that would prevent or restrict participation in the audiological evaluations and clinical trial.
- 4. Hearing loss of neural or central origin.
- 5. Unrealistic expectations on the part of the candidate and/or candidate's family, regarding the possible benefits, risks, and limitations that are inherent to the surgical procedure(s) and prosthetic devices.

- 6. Unwillingness or inability of the candidate to comply with all investigational requirements.
- 7. Active middle ear infection.

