# 1.3 Investigational Procedure

## 1.3.1 Design Overview:

The study will be conducted as a repeated-measure, single-subject experiment. A single-subject research design (in which each participant serves as his or her own control) is appropriate because it accommodates the heterogeneity that characterizes hearing-impaired populations. Blinding or masking procedures are not included in the design, as it is not possible to conceal the presence or absence of a cochlear implant from device recipients and/or clinical investigators.

Preoperatively, candidates will be assessed with their current amplification to evaluate their appropriateness for entrance into the study. The candidates' audiometric configuration must meet the above inclusion criteria. That is, the candidate must have a profound sensorineural hearing loss from 250 to 8000 Hz. Prior to testing, the appropriateness of the hearing aid fitting will be assessed and adjustments made if necessary. In cases where amplification has not been used for more than one year, new hearing aids will be fit, worn for a minimum three-month trial and the participants re-evaluated to confirm continuance with the study.

Fifteen infants will receive one Nucleus L24 array and a FDA approved standard-length array on contralateral ears. We will alternate every other subject between the right and left ears as to which ear gets the Nucleus L24. Postoperatively, the right ear only, left ear only, and the bilateral listening modes will be compared with repeated testing through five years of age of the child. These comparisons will help to evaluate the effects of bilateral stimulation using a shorter electrode cochlear implant to possibly preserve the scala media, organ of Corti, and supporting cells for future medical interventions and a standard length implant on the contralateral ear. In addition, we will attempt to compare speech perception and speech/language measure results with age-matched children implanted with standard-length bilateral devices. The following defines the various modes referenced throughout the course of this text:

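### The external comparators are specified only by device and age-matching, while L24 children must meet prognostic entry criteria, so the between-group comparison is open to selection bias of undetermined direction

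*Combined protocol and SAP*

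**What the plan says.** The protocol names two external comparator groups.

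- **Two standard-length arrays.** Section 1.3.1: "we will attempt to compare speech perception and speech/language measure results with age-matched children implanted with standard-length bilateral devices". Section 1.8 repeats this: "We will attempt to compare these results with age-matched children implanted with standard-length bilateral devices on both ears".
- **Standard plus S12.** Section 1.8, if possible: "age-matched children implanted with a standard-length device on one ear and a Nucleus S12 implant on the contralateral ear".

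For neither group does the plan give a source, period, number, eligibility rule, further matching factor or covariate adjustment. It does not say whether the age matched is age at implantation or at test.

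Entry to the L24 group is much more closely defined. Section 1 lists profound bilateral sensorineural loss, no benefit from well-fitted hearing aids, "language deficit; and supportive family dynamics". Section 1.1 adds profound thresholds from 250 to 8000 Hz in both ears, a monolingual English-speaking family, a three-month hearing aid trial, and "Patent cochlea and normal cochlear anatomy as shown by a CT scan". Section 1.2 excludes cochlear anomalies that might prevent full insertion, loss of neural or central origin, and "Developmental disabilities or other conditions that would prevent or restrict participation in the audiological evaluations and clinical trial".

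On size, section 1.8 says "we will only be implanting up to 15 infants with Nucleus L24 and standard-length electrode arrays on contralateral ears" and concedes that power may be too low for some questions. It does not mention confounding of the external comparison.

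**The concern.** Section 1.8 measures success on speech perception and speech/language tests given in English. Scores on such tests plausibly depend on the characteristics that sections 1, 1.1 and 1.2 control in the L24 group. Nothing carries those criteria over to the comparators. Read as written, an age-matched child with two standard arrays from a bilingual home, with an abnormal cochlea or with less than profound loss at some frequencies would satisfy the stated rule.

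A difference between groups, or its absence, could then reflect who was compared and not which arrays they received. A shortfall of the L24 configuration might be masked, or one might appear where none exists. More children would not cure this, so the caveat about power does not cover it. Even a perfect age match would leave the selection difference in place.

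**Working it through.** The plan gives no effect size, SD, significance level, comparator number or model, so there is no figure to reproduce. The limit of 15 infants is a feasibility cap.

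**Step 1. Which outcomes depend on the external group (sections 1.5.4.1 and 1.5.4.2)**

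| Outcome | Listening condition | Contrast of L24 ear with standard ear in the same child? |
|---|---|---|
| Iowa vowel test, ESP, PB-K | Unilateral and bilateral | Yes |
| GASP, MLNT/LNT | Bilateral | No |
| All speech/language tests | Bilateral | No |

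For the last two rows the external group is the only device comparison. For every outcome, it is also the only way to set L24-plus-standard against two standard arrays.

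**Step 2. Which way each L24 criterion could push the comparison, if comparators are not held to it**

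- Could favour L24: monolingual English home, normal cochlea, no restricting developmental disability, no neural or central loss, supportive family.
- Could act against L24: profound loss across 250 to 8000 Hz, no hearing aid benefit, language deficit at entry.

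**Step 3. Net bias (illustrative; all inputs assumed)**

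Let f be the excess share of comparators with a trait that lowers the outcome by d SD, and g the excess share with an advantage, such as residual hearing, that raises it by e SD. The bias toward L24 is B = f × d − g × e.

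- f = 0.2, d = 0.5, g = 0: B = 0.2 × 0.5 = +0.10 SD
- f = 0.3, d = 1.0, g = 0: B = 0.3 × 1.0 = +0.30 SD
- f = 0.3, d = 1.0, g = 0.3, e = 1.0: B = 0.30 − 0.30 = 0
- f = 0.1, d = 1.0, g = 0.4, e = 1.0: B = 0.10 − 0.40 = −0.30 SD

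The sign depends on comparator characteristics that the documents do not give.

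**Step 4. Consequence for a test with no true device effect**

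Assume SD 1, two-sided 5% level, a normal approximation, and 15 L24 children against m comparators. Then SE = √(1/15 + 1/m), and the rejection probability is [1 − Φ(1.96 − B/SE)] + Φ(−1.96 − B/SE).

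| m | SE | B = 0 | B = ±0.3 | B = ±0.5 |
|---|---|---|---|---|
| 15 | 0.365 | 5.0% | 13.0% | 27.8% |
| 30 | 0.316 | 5.0% | 15.8% | 35.3% |

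For example, with m = 15 and B = +0.3, B/SE = 0.82. The chance of a false finding that L24 is better is 12.7% and that it is worse is 0.3%, total 13.0%. Reversing the sign of B swaps the two. Increasing the comparator number raises the error rate, because a fixed bias is then estimated more precisely.

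**Step 5. Consequence for a descriptive reading**

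At 15 against 15, the difference detectable with 80% power is (1.96 + 0.84) × 0.365 ≈ 1.02 SD. Moderate differences will mostly be judged from the estimates, which carry B in full: +0.30 SD would exactly cancel a true L24 deficit of 0.30 SD.

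**The case against.** Four points can fairly be made for the plan.

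- **The direction is not shown.** A reader might infer that the comparison is biased in favour of L24, because those children were screened. That overlooks the criteria in Step 2 that could work the other way. Section 1 itself pairs language deficit with family support. This objection stands.
- **Silence is not a waiver.** A reader might infer that comparators will be chosen on age alone and that anyone may enter. The plan states no other criterion, but it does not say that others will be ignored, and it does not describe how the S12 children were selected. The same measures must also be used, so children unable to complete the battery contribute no data on it, although a child whose testing is only restricted could remain. This stands as a limit on the wording. It does not supply the missing rule.
- **The design is within-child.** A reader might infer that any deficit of the shorter array could be hidden. On the vowel test, ESP and PB-K, each child's two ears are compared directly, and comparator choice cannot affect that. This stands for those tests only.
- **The comparison is tentative.** The study will only attempt it, and it is feasibility work. That bears on how serious the gap is. However, section 1.8 ties success to these measures, and its independent variable, though garbled in wording, is the configuration that a child receives, which is a between-child factor. The external comparison is therefore not peripheral.

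**Conclusion.** The concern holds in this form: device and age-matching are the only selection factors stated for either external comparator, the L24 children are selected on several prognostic criteria, and no restriction or adjustment bridges the two. The comparison is therefore open to selection bias, mainly for the bilateral-only outcomes and for any statement about two standard arrays.

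Neither direction nor size can be determined from the documents. The range of −0.30 to +0.30 SD and the error rates above show what plausible imbalances would do; they rest wholly on assumed shares, effects and comparator numbers. The documents do not support a claim that the bias favours L24, or that ear-level deficits would be concealed.

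This is worth correcting in a feasibility study because the remedy is cheap and works whichever way the bias runs. It does not undermine the within-child part of the design.

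**What to change.** In sections 1.3.1 and 1.8, define both comparator groups along these lines:

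> Age-matched children with the stated devices whose records at implantation show that they meet inclusion criteria 2, 3, 5 and 6 of section 1.1 and none of exclusion criteria 2, 3 and 4 of section 1.2. Comparator eligibility will be decided before outcome scores are examined.

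This covers criteria that could push the result either way: degree and type of loss and the hearing aid trial, as well as home language, anatomy, development and site of lesion. Deciding eligibility first prevents comparators from being chosen with knowledge of their results.

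The rule does not equalise family support, hearing aid benefit or baseline language. Section 1.8 should say that differences in these may remain, and should describe the external comparison as exploratory.

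The cost is a short text change, a chart check for each candidate comparator, and a smaller pool. The check may be limited by what the records hold, for example on home language, the hearing aid trial or a full audiogram. No change to the L24 group or its testing is needed.
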